1. SYNOPSIS

Hemanext Inc. [name] United States of America "A Single Center, Pilot Clinical Investigation of Surgcal Bleeding in Burn Patients, and Chronically Transfused Patients with Haematologic Malignancies, who are Transfused with Hypoxic Red Blood Cells Manufactured with Hemanext ONE system"
[name] United States of America "A Single Center, Pilot Clinical Investigation of Surgcal Bleeding in Burn Patients, and Chronically Transfused Patients with Haematologic Malignancies, who are Transfused with Hypoxic Red Blood Cells Manufactured with Hemanext ONE system"
United States of America "A Single Center, Pilot Clinical Investigation of Surgcal Bleeding in Burn Patients, and Chronically Transfused Patients with Haematologic Malignancies, who are Transfused with Hypoxic Red Blood Cells Manufactured with Hemanext ONE system"
"A Single Center, Pilot Clinical Investigation of Surgcal Bleeding in Burn Patients, and Chronically Transfused Patients with Haematologic Malignancies, who are Transfused with Hypoxic Red Blood Cells Manufactured with Hemanext ONE system"
Transfused Patients with Haematologic Malignancies, who are Transfused with Hypoxic Red Blood Cells Manufactured with Hemanext ONE system"
Transfused Patients with Haematologic Malignancies, who are Transfused with Hypoxic Red Blood Cells Manufactured with Hemanext ONE system"
Cells Manufactured with Hemanext ONE system"
"Hypoxic Red Blood Cells for Burns and Hematological Malignancies at Haukeland University Hospital"
"Hypoxic Red Blood Cells for Burns and Hematological Malignancies at Haukeland University Hospital"
CLIN-0012
PRO-CLIN-0012 Rev. AA dated 25 April 2022
Hemanext Inc. will comply with the Research Council of Norway on requirements and guidelines for
registration and disclosure of medical and health-related studies involving human participants, through:
www.ISRCTN.org
Medical device:
Hemanext ONE – A blood container set used to process and store CPD/PAGGSM Red Blood Cells,
Leukocytes Reduced, and O ₂ /CO ₂ Reduced.
UDI number : 0856186008TECH-0001W9
Manufacturer:
Hemanext Inc.
[name]
[name]
[name]
USA
Medical device:
Hemanext ONE
CE Marked since April 2021 (Post-Market stage)
Blood Product:
CPD/PAGGSM Red Blood Cells, Leukocytes Reduced, and O ₂ /CO ₂ Reduced
The Norwegian National Directorate of Health will be notified that this blood product is under evaluation.
In Norway, this blood product is currently not registered with the Norwegian Directorate of Health (Helsedirektoratet).
1. Background and rationale for hypoxic blood use:

Red blood cells (RBCs) comprise the only tissue in the body that provides oxygen transport. Anemia results from either the acquired loss of RBCs due to disease, injury, or surgery or the inability of the patient to produce their own RBCs due inherited disorders. While the overall clinical settings of anemia can differ greatly between acute or chronic causes, the primary therapeutic goal of RBC transfusion is to increase the oxygen-carrying capacity and prevent tissue hypoxia¹. Red blood cells can be stored for up to 42 days before transfusion but, surprisingly, there are few quality parameters that predict the efficacy and safety of a transfusion².

2. Consequences of Current RBC Storage Process

A review of the literature^{2,3,4,5} identifies substantial evidence suggesting decreased quality of RBCs from substances that accumulate during RBC storage. These include nitric oxide (NO) scavengers and inhibitors of NO generation that affect vascular tone, procoagulant microparticles, free and non-transferrin bound iron, and bioactive lipids. Additionally, RBCs show progressively diminished deformability over time, characteristics necessary to adequately perfuse the microcirculation⁴. D'Alessandro and colleagues observed significant changes in the plasma levels of hemolytic markers, oxidized purines, plasticizers, and oxidized lipids in recipients of blood stored for 42 days, compared with 5 days³.

Yoshida and colleagues performed an exhaustive review of the oxidative and metabolic changes that occur to RBCs during storage, summarizing elements of the RBC storage lesion from causes to associated clinical sequelae. The review identifies root causes, effects on RBCs, physiological consequences reported from in vitro experiments or animal models, and finally, potential clinical sequelae of RBC transfusion, each element being identified with its pertinent reference(s)².

3. Hypoxic storage and HEMANEXT blood product

Hypoxic storage, where the oxygen content of RBC units is reduced to low levels [e.g., less than 20% oxy-hemoglobin (SO₂)⁶ prior to refrigeration and maintained throughout storage], was proposed as an alternative to antioxidant-based additive solutions to reduce oxidative stress during hypothermic RBC storage^{5,7-11}. The rationale for implementing hypoxic storage is to reduce oxygen, the essential substrate for hemoglobin oxidation that generates the multitude of untoward physiologic and biochemical events described previously.

Hypoxic storage was also shown to counteract some metabolic impairments without requiring novel additive ingredients^{5,7} independent of the reduction in oxidative stress. During pre-storage processing to reduce oxygen content in the RBC, carbon dioxide is also reduced. Carbon dioxide depletion increases cytosolic pH that was lowered from its physiological level by exposure to acidic anticoagulant and additive solutions. The resulting more neutral pH in the early phase of storage results in sustained flux through the glycolytic pathway and elevated 2,3-DPG levels, which are highly sensitive to pH and normally depleted early during hypothermic storage^{7,11,12}. Additionally, deoxyhemoglobin causes metabolic modulation to release glycolytic enzymes, such as phosphofructokinase and glyceraldehyde dehydrogenase, sequestered at the band 3 binding domain, thereby enhancing overall glycolytic flux during hypoxic storage^{13,14}.

Metabolomics work by D'Alessandro et al has shown that hypoxic storage diminishes damaging mediators of oxidative stress and increases energy biomarkers without requiring novel additive ingredients¹⁵. The same group investigated the metabolomics of hypoxic storage in a two-arm cross-sectional clinical study. Hypoxic storage was found to ameliorate the metabolic phenotypes of stored RBCs (lower markers of oxidant stress such as lipids and purines and higher levels of high-energy phosphate compounds) and improve post-transfusion recovery (PTR). The study also correlated metabolic parameters to hemolysis and PTR, highlighting the role of purine and lipid oxidation (e.g., hypoxanthine and 9-HODE), so that these can be used as markers in fresh and stored units to predict end of storage blood quality¹⁵.

Population:

The Hemanext ONE System may be used to manufacture hypoxic RBCs for any patient requiring a blood transfusion. This pilot investigation aims to study safety of hypoxic RBCs in 2 patient groups: acute burn and hematologic malignancies. Burn patients undergoing surgical excision routinely require large quantities of blood to be transfused. Those patients with hematologic malignancies often require regular transfusions.

Burn Patients

Major burn trauma has been found to trigger an inflammatory cascade of events which leads to oxidative stress and tissue damage. These injurious responses, which include complement activation, excessive histamine release, decreased blood pressure, and release of reactive oxygen species, may ultimately lead to the development of multiple organ dysfunction¹⁶. Early excision and grafting of large burn wounds is currently performed to attenuate the post-burn hypermetabolic state and remove the biological nidus for infection. These operative procedures can result in considerable bleeding. In one report, intraoperative blood loss was estimated at approximately 9.2% of blood volume for every 1% of total body surface area (TBSA) burn excised²⁰.

Patients with Hematological Malignancies

Hematologic malignancies such as myelodysplastic syndromes (MDS), multiple myeloma, and leukemia are increasing in prevalence in Norway. Collectively, hematologic malignancies refers to various disorders of the bone marrow which result in abnormal blood cell production. Leukemia presents with increased numbers of leucocytes in the blood and bone marrow²³. Multiple myeloma is characterized by uncontrolled growth of plasma cells in the bone marrow. MDS consist of bone marrow diseases associated with ineffective hematopoiesis, resulting in morphologically abnormal blood cells²⁴. In all cases, anemia can result from the overcrowding or ineffective production of normal blood cells, leading to inadequate oxygen delivery. Patients often require regular blood transfusions at some time during their treatment to alleviate the symptoms of severe anemia, which can include fatigue, weakness, and exacerbation of other underlying medical conditions. The treatment goal is to minimize morbidity and mortality with the lowest possible exposure²⁶. Some studies show reduced survival with increased transfusion density²⁷. Iron overload with organ impairment, a consequence of transfusion dependency, may be fatal in those who are heavily iron-overloaded^{28,29}. Therefore, where a patient has no fatigue-induced limitation on quality of life or function at home, a more conservative approach may be preferred to avoid potential adverse effects and improve outcomes³¹.

Potential B enefits of Hypoxic RBC Use

In vitro and pre-clinical data support the hypothesis that hypoxic blood carries the potential to benefit patients suffering from hematological malignancies and burn injuries. Hypoxic storage may reduce oxidative stress, as shown in metabolomics work by D'Alessandro et al highlighting diminished mediators of oxidative stress in hypoxically stored blood vs conventional¹⁵. The use of hypoxically stored blood may improve oxygen delivery, as evidenced in CLIN-0001 signifying that hypoxically stored blood showed improvements in ATP, 2,3 DPG, and RBC deformability³². The increases in 2,3 DPG levels contribute to a rightward shift of the O₂ dissociation curve, which may translate to improved oxygen delivery³⁴. Additionally, hypoxically stored blood may decrease the required number of RBC transfusions. A study by D'alessandro et al demonstrates that hypoxic storage yields more viable RBCs, as indicated by greater PTR24 values¹⁵. The increase in viable RBCs demonstrated in the aforementioned study supports a potential 15% reduction in blood requirements for both patient groups¹⁵. Because transfusion-related iron overload is directly associated with the number of RBC units transfused in patient who require chronic transfusions, this reduction in blood requirements may lead to lower transfusion density and decreased risk of iron overload^{5,9} in patients with hematological malignancies. Furthermore, hypoxic blood may improve resuscitation time and/or volume in burn patients, as demonstrated in a pre-clinical animal model of resuscitation from hemorrhagic shock³⁵.

Objective(s):	Primary Objective – for both patients groups	
	Hypoxic RBCs safety and tolerance assessment up to 24 hours following the transfusion initiation and overall up to 7 days (+/- 1 day) after the transfusion episode (single transfusion course).	
	Secondary Objectives :	
	A. For both patients groups	
	 Assessment of pre and post transfusion hemoglobin levels Assessment of hemoglobin level before the following transfusion, if applicable Assessment of AEs occurence: Up to 7 days (+/- 1 day) post transfusion, in comparison with historical control (including but not limited to infection, deep vein thrombosis, acute respiratory distress syndrome, transfusion-related acute lung injury, transfusion associated circulatory overload, anaphylactic shock, acute haemolytic transfusion reaction). 	
	 Up to the subsequent transfusion episode or up to 28 days (+/- 1 day) after the initial transfusion, whichever comes first. 	
	iii. From enrollment, up to their subsequent transfusion or 28 days (+/- 1 day) post transfusion, whichever comes first, through the assessment of patient's diary	
	4. Assessment of the vital signs during and up to 15 minutes after the transfusion	
	B. For burn patients group only:	
	 Assessment of arterial blood gases: pre-operative intra-operative post operative 	
Outcome(s):	Primary Outcome – for both patients groups	
	Number of participants who experienced an adverse event (all types/grades) within a time frame up to 24 hours following the transfusion and overall up to 7 days (+/- 1 day) after the transfusion.	
	 The type and the grade of each adverse event will be categorized according to: Association for the Advancement of Blood and Biotherapies (AABB) technical manual, 20th edition (2020) Biomedical Excellence for Safer Transfusion (BEST) Collaborative review - Lancet 2016; 388: 2825–36 Local AEs database (for reference) ISO 14155-2020 definitions 	
	Secondary Outcomes : - for both patients groups	
	 Evolution of the hemoglobin level before and after the transfusion. Calculation oft he Hemoglobin increment after transfusion corrected for patient blood volume and hemoglobin dose Comparison of the Hemoglobin level before the index transfusion to that prior to the 	

	 subsequent transfusion 4. Comparison of the frequency of all AEs, including transfusion related AEs up to 7 days (+/- 1) post-transfusion compared to historical data in local patient registries (ex. The National Burn Registry) 5. Evaluation of AEs from enrollment, up to prior to the subsequent transfusion or up to 28 days (+/- 1 day) after the initial transfusion, whichever comes first. 6. Evaluation of the frequency of all AEs, from enrollment, up to their subsequent transfusion or 28 days (+/- 1 day) post-transfusion, whichever comes first, through the assessment of patient's diary, when applicable. 7. Evaluation of patient's vital signs over the course of the transfusion and up to 15 minutes post-transfusion
Design:	"A single center, pilot clinical investigation of surgical bleeding in burn patients, and chronically transfused patients with haematologic malignancies, who are transfused with hypoxic red blood cells manufactured with Hemanext ONE system".
	A first cohort of 5 patients – solely from the hematological malignancies (chronically transfused) group - will be enrolled, transfused and followed-up until their subsequent transfusion or 28 days (+/- 1 day) post-transfusion, whichever comes first
	All safety related data from this initial cohort of 5 patients will be reviewed and assessed by the clinical investigation Data Monitoring Committee (DMC).
	•
	Upon favourable opinion from the clinical investigation DMC, the enrolment of the remaining patients (both groups) will resume until completion.
	Day 0 Planned Transfusion Episode Day 7 Day 28*
	Pt. Screening Enrollment Day 1 (+/- 1 day) (+/- 1 day)
	Visit 0 (V0) Visit 1 (V1) Visit 2 (V2) Visit 3 (V3) Visit (V4) Last Visit (V5)
	Pt. Information Pt. consent Transfusion Phone call On site visit
	BURN – 2 units Hemanext / xx standard units
	HEMATOLOGY – 2+ units Hemanext
	NB: * Day 28+/- 1 day or next transfusion episode, whichever happens first.
Inclusion / exclusion criteria:	INCLUSION CRITERIA
	Patients meeting the following criteria may be invited to participate in the clinical investigation and

	undergo the informed consent process:					
	 A. Hematological malignancies patients group: Male or female patients at least 18 years of age Patients expected to require ≥ 2 units of red blood cells in a single transfusion event Patients who have the capacity to consent to particpate and are willing to comply with the study procedures. Patients identified by a Transfusion hemoglobin trigger of less than 9 g/dL Patients with a documented diagnosis of leukemia, myelomatosis or MDS requiring chronic transfusions 					
	 B. Burn patients group: Male or female patients at least 18 years of age Patients who have the capacity to consent by themselves to participate to the clinical investigation Smaller burn patients, hospitalized with a Total Body Surface Area (TBSA%) burn ≥ 10% and ≤ 50% Patients expected to require ≥ 2 unit of red blood cells in a single transfusion event 					
	EXCLUSION CRITERIA					
	Patients meeting any of the exclusion criteria may not participate in the clinical investigation.					
	A. Both patients groups					
	 Patients with any positive antibody screening test Patients for whom consent has not been obtained Patients with a known hemolytic anemia (congenital or acquired) Patients < 18 years old Patients with a known or suspected pregnancy Patients with a history of major transfusion reactions Patients whom the Investigator deems clinical trial participation is not in their best interest. 					
	 B. Burn patients specific exclusion criteria : Patients who do not have the capacity to consent by themselves to participate to the clinical investigation Patients hospitalized with a Total body surface area (TBSA%) burn more than 50% Patients with combined trauma in need of blood transfusions for treatment other than the burn excision 					
Measurements and procedures:	The following information will be collected, from enrollment throughout end of study visit, when applicable:					
	 Informed consent Documentaton of Inclusion/Exclusion criteria Demographics Medical history Physical examination Pregnancy test (if applicable) Height Weight RBC unit weight and volume Age (days) of the RBC unit at the time of the transfusion Hemoglobin measurement - maximum 4 hours before the transfusion and, at minimum, 15 minutes before transfusion Hemoglobin measurement 15 to 60 minutes after transfusion Hemoglobin measurement, at a minimum, 15 minutes before the following transfusion 					

	14. Blood pressure every 15 minutes during the transfusion and until 15 minutes after the end of the transfusion
	15. Heart rate every 15 minutes during the transfusion and until 15 minutes after the end of the transfusion
	 Body temperature every 15 minutes during the transfusion and until 15 minutes after the end of the transfusion
	17. Respiratory rate every 15 minutes during the transfusion and until 15 minutes after the end of the transfusion
	 18. Oxygen saturation every 15 minutes and until 15 minutes after the end of the transfusion
	 19. Patient diary for collection of concomittant medications and changes in health status from enrollment up to their subsequent transfusion or 28 days (+/- 1 day) post-transfusion, whichever comes first 20. Routine laboratory analyses, including blood gases when applicable.
Intervention:	For both clinical investigation patient populations:
	 Transfusion of two units of Red Blood Cells, Leukocytes reduced, O₂/CO₂ reduced (single transfusion course) manufactured with the Hemanext ONE System, combined with PRN standard Red Blood Cells, as applicable. Patient's diary
Control intervention (if applicable):	Not applicable
Number of subjects with rationale:	10 acute burn patients and 10 patients with haematological malignancies, who require transfusion of red cells concentrates and who fulfil all eligibility criteria will be enrolled in this clinical investigation at Haukeland University Hospital.
	A total of twenty patients will be sufficient to assess preliminary safety of O ₂ /CO ₂ reduced RBCs, as the standard rate of transfusion related adverse events is usually low and these expected events are well known. If any unexpected adverse events (any type or grade) should occur, they will be identified as such.
Duration of the investigation:	This clinical investigation is estimated to last for a period of approximately 6 months.
Investigation	Anticipated Start Date: May – June 2022
schedule:	Anticipated End Date: November – December 2022
Investigator(s):	Principal Investigator: [name]
	Address: Haukeland University Hespital [name]
	Haukeland University Hospital, [name]
	Norway
	Phone:
	E-mail:

	Sub-Investigator: [name] Address : Haukeland University Hospital, [name] Norway E-mail:
Investigational Site(s):	This clinical investigation will only involve one single clinical site:
	Haukeland University Hospital [name] Norway
Blood Bank	Oslo: Address: Department of Immunology and Transfusion Medicine Section for Blood processing Oslo University Hospital Ullevål Norway
	Bergen: Address:
	Address: Haukeland University Hospital Department of Immunology and Transfusion Medicine [name] Norway E-mail:
Data Monitoring Committee (DMC)	Membership: Professor of intensive care medicine

	Haukeland University Hospital, Bergen
	Chief of Burns, Plastic and reconstructive surgeon
	Haukeland University Hospital, Bergen
	Pland Pank, Haukaland University Heanital, Person
	Blood Bank - Haukeland University Hospital, Bergen
	Blood Bank - Haukeland University Hospital, Bergen
	Blood Bank - Haukeland University Hospital, Bergen
Statistical considerations:	This clinical investigation is not statistically powered – only descriptive statistical methods will be applied
Compliance statement:	This investigation will be conducted in compliance with the CIP, the current version of the Declaration of Helsinki, ISO14155-2020, ICH-GCP (as far as applicable) as well as all national legal and regulatory requirements.

Hematogical Malignancies Group:

Investigation Periods	Screening & Enrollment Visit	Pre- Transfusion	Transfusion	Post- Transfusion	Follow Up 1	Follow-up 2	Follow-up 3
Visit	1	2	2	2	3	4	5
Time (hour, day, week)	D0	D1	D1	D1	D2 (≤ 24h)	D7 (+/- 1 day)	Day of subsequent transfusion or D28, whichever comes 1st
In- /Exclusion Criteria	x	x					
Patient Information							
Patient Information and Consent (ICF)	x						
Demographics	x						
Medical History	x						
Concomitant Medications	x	х	x	x	x	x	х
Physical Examination	x						x
Pregnancy Test	x						
Height	x						
Weight	x						
RBC Unit Weight		x					
Patient Hemoglobin		x		x			x
Blood Pressure	x	x	x	x			
Heart Rate	x	x	x	x			
Body Temperature	x	x	x	x			
Respiratory Rate	x	x	x	x			
Oxygen Saturation	x	x	x	x			
Transfusion			x				
Adverse Events, Adverse device effects	x	x	x	x	x	x	x
Review HSB (blood bag) Integrity		x	x	x			
Patient Diary	x	x	x	x	x	x	x

Burn patients Group:

Investigation Periods	Screening & Enrollment ∀isit	Pre- Transfusion	Transfusion	Post- Transfusion	Follow Up 1	Follow-Up 2	Follow-Up 2
Visit	1	2	2	2	3	4	5
Time (hour, day, week)	Day 0	Day 1	Day 1	Day 1	Day 2 (≤ 24 h)	Day 7 (+/- 1 day)	Day of subsequent transfusion or D28, whichever comes 1st
In- /Exclusion Criteria	x						
TBSA	x						
Patient Information							
Patient Information and Consent (ICF)	x						
Demographics	x						
Medical History	x						
Concomitant Medications	x	x	x	x	x		x
Physical Examination	x						x
Pregnancy Test	x						
Height	x						
Weight	x						
RBC Unit Weight		x					
Patient Hemoglobin		x		x			x
Blood Pressure	x	x	x	x			
Heart Rate	x	x	x	x			
Body Temperature	x	x	x	х			
Respiratory Rate	x	x	x	x			
Oxygen Saturation	x	x	x	x			
Transfusion			x				
Adverse Events, Adverse device effects	x	x	x	x	x		x
Review HSB (blood bag) Integrity		x	x	x			

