5.1.5 Background on Blood Use in Hematological Malignancies:

Hematologic malignancies such as myelodysplastic syndromes (MDS), multiple myeloma, and leukemia are increasing in prevalence in Norway as the population average age continues to increase. Collectively, hematologic malignancies refers to various disorders of the bone marrow which result in abnormal blood cell production. Leukemia consists of several malignant disorders that present with increased numbers of leucocytes in the blood and bone marrow²³. Multiple myeloma is characterized by uncontrolled growth of plasma cells in the bone marrow. MDS consist of bone marrow diseases associated with ineffective hematopoiesis, resulting in morphologically abnormal blood cells²⁴. In all cases, anemia can result from the overcrowding or ineffective production of normal blood cells, leading to inadequate oxygen delivery.

Patients with hematologic malignancies often require regular blood transfusions at some time during their treatment to alleviate the symptoms of severe anemia, which can include fatigue, weakness, and exacerbation of other underlying medical conditions. While treatment varies with disease severity, transfusions are given at approximately weekly intervals in intensive treatment²⁵. In relying on stored donor RBCs to address anemia, the goal is not to rapidly rebuild a normal red cell mass, but to minimize morbidity and mortality with the lowest possible exposure²⁶. No consensus exists on the appropriate time to commence transfusions or on the correct transfusion threshold for optimal care. Some studies show reduced survival with increased transfusion density²⁷. Iron overload, a consequence of transfusion

dependency, is also independently associated with poor outcomes for patients with MDS^{28,29}. Iron overload with organ impairment may be fatal in those who are heavily iron-overloaded³⁰. Therefore, where a patient has no fatigue-induced limitation on quality of life or function at home, a more conservative approach may be preferred to avoid potential adverse effects and improve outcomes³¹.

[figure not shown]

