7. CLINICAL INVESTIGATION OUTCOMES

7.1 Primary Outcome

Primary Outcome – for both patients groups

Number of participants who experienced an adverse event (all types/grades) within a time frame up to 24 hours following the transfusion and overall up to 7 days (+/- 1 day) after the transfusion.

The type and the grade of each adverse event will be categorized according to:

- Association for the Advancement of Blood and Biotherapies (AABB) technical manual, 20th edition (2020)
- Biomedical Excellence for Safer Transfusion (BEST) Collaborative review Lancet 2016; 388: 2825–36
- Local AEs database (for reference)
- ISO 14155-2020 definitions

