3.3 Clinical investigation outcomes

3.3.1 **Primary outcome**

Number of participants who experienced an adverse event (all types/grades) from transfusion up to 24 hours and 7 days (+/- 1 day) post transfusion.

3.4 Secondary Outcomes:

1. Evaluation of blood pH, pO2, pCO2, HCO3 and base (excess) before, during and after the transfusion (Burn patients group only).

LINK Medical Study ID: HEM001

- 2. Hemoglobin level before the following transfusion
- 3. Frequency of all AEs, including transfusion related AEs up to 7 days (+/- 1) post-transfusion
- 4. AEs up to 28 days after the initial transfusion, or up to subsequent transfusion episode, whichever comes first.
- 5. Frequency of all AEs, from enrollment, up to 7 days (+/- 1 day) post transfusion, through the assessment patient's diary, when applicable.
- 6. Vital signs over the course of the transfusion and up to 15 minutes post-transfusion.

4 Study Design

This is a single center clinical trial of surgical bleeding in burn patients, and chronically transfused patients with haematologic malignancies. Patients are transfused with hypoxic red blood cells manufactured with Hemanext ONE system". The patient groups are burn patients and chronically transfused patients with haematologic malignancies. Patients need to be adults \geq 18. There will be no randomization of Patient s, no blinding, and no comparator.

A first cohort of 5 patients – solely from the hematological malignancies (chronically transfused) group - will be enrolled, transfused and followed-up until their subsequent transfusion or 28 days (+/- 1 day) post-transfusion, whichever comes first. All safety related data from this initial cohort of 5 patients will be reviewed and assessed by the clinical investigation Data Monitoring Committee (DMC). Upon favourable opinion from the clinical investigation DMC, the enrolment of the remaining patients (both groups) will resume until completion.

Each patient is expected to attend 5 visits:

- 1. Visit 1 (Screening): Determine eligibility and obtain baseline data, physical examination, and safety assessments.
- 2. Visit 2 (Transfusion Day):
 - a. Pre-Transfusion: eligibility, hemoglobin, and safety assessments
 - b. Transfusion: transfusion, safety assessments, and device integrity
 - c. Post-Transfusion: safety assessments, hemoglobin, and device integrity
- 3. Visit 3 Follow-Up (24 hours post-transfusion): safety assessments and device integrity

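### The DMC gate sets no minimum follow-up, so a cohort patient re-transfused before Day 7 can meet it with an incomplete primary safety window

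*Protocol*

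**What the plan says.** The Protocol synopsis (Design) opens the trial with "A first cohort of 5 patients", all from the chronically transfused haematology group. They "will be enrolled, transfused and followed-up until their subsequent transfusion or 28 days (+/- 1 day) post-transfusion, whichever comes first". SAP 4 repeats the rule: "followed-up until their subsequent transfusion or 28 days (+/- 1 day) post-transfusion, whichever comes first". The DMC then reviews the cohort's safety data, and "Upon favourable opinion from the clinical investigation DMC, the enrolment of the remaining patients (both groups) will resume until completion". Neither document adds a minimum number of days, a completed Day 7 contact, or a number of patients with a full window.

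The primary outcome counts patients with an adverse event "within a time frame up to 24 hours following the transfusion and overall up to 7 days (+/- 1 day) after the transfusion" (Protocol 7.1). Protocol 5.5 stops adverse event collection in haematology patients at the next transfusion or Day 28, whichever is earlier. Protocol 11.2.1 and 11.3.5 plan a phone contact at Day 7 (+/- 1) and attach no condition to it.

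On how soon these patients return, the only figure is in Protocol 5.1.5: "transfusions are given at approximately weekly intervals in intensive treatment".

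**The concern.** The gate closes for each patient at whichever of two events comes first, and one of them, the next transfusion, can come at any time. The cohort is drawn only from people who are transfused repeatedly, so the more heavily transfused the patient, the less follow-up the gate asks for. A patient could count as finished for the DMC while the trial's own primary safety measure is still open.

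This is the only scheduled safety hold. Protocol 13.4.4 plans no interim analysis, Protocol 13.3 sets no statistical stopping criterion, and the suspension powers in Protocol 10.2 are ad hoc. Behind the gate stand 15 patients, including all ten burn patients. Protocol 8.1 describes the study as the first use of the product. The human experience reported in Protocol 5.4 is 14 people given about 10 mL of autologous cells in a different additive solution. The Protocol itself expects delayed as well as acute transfusion effects (12.3), so the later days of the first week matter.

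**Working it through.** **Figures in the plan.** 10 + 10 = 20 patients; 20 - 5 = 15 after the gate (5 haematology, 10 burn). No rate, power or decision criterion is stated, so there is no gate calculation to reproduce. Day 7 below means seven days after transfusion.

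**The texts side by side.**

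| Place | Rule | Makes the gate wait for Day 7? |
|---|---|---|
| Synopsis Design; SAP 4 | Cohort follow-up ends at the earlier of next transfusion and Day 28 (+/- 1) | No |
| Protocol 5.5 | Haematology adverse event collection ends at the same point | No |
| Protocol 7.1 | Primary window closes on Day 6 to 8 | Not linked to the gate |
| Protocol 11.2.1, 11.3.5 | Day 7 (+/- 1) phone contact, unconditional | Not linked to the gate |
| Protocol 11.3.6 | Final follow-up is the next transfusion visit or Day 28 | No |
| Protocol 13.5 | Drop-outs are contacted about the 7 days (+/- 1), and beyond that to the next transfusion or Day 28 | Not linked to the gate |

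Take a cohort patient re-transfused on Day 4. Gate follow-up, adverse event collection under 5.5 and the final visit all fall on Day 4. The Day 7 contact is due on Day 6 to 8, so the window is 2 to 4 days short (6 - 4 and 8 - 4). No text says which rule governs.

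**How likely is a cut window?** Let q be the chance that a patient is re-transfused before Day 7. The documents do not give it. The chance that at least one of five is cut is 1 - (1 - q)^5:

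- q = 0.05: 22.6%
- q = 0.10: 41.0%
- q = 0.20: 67.2%
- q = 0.30: 83.2%
- q = 0.50: 96.9%

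With normally distributed intervals (assumed), a mean of 7 days gives q = 0.50 and 96.9%. A mean of 14 days with SD 4 gives q = 0.04 and 18.5%. A mean of 21 days with SD 4 gives about 0.1%. If the window is taken to close at Day 6, the earliest permitted contact, a mean of 7 days gives 57.8% (SD 1) to 92.3% (SD 4).

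**What does a cut window cost?** Assume a per-patient reaction risk p spread evenly over seven days, and k of the five patients cut at 3.5 days. The 3.5 days is an assumption with no source in the documents. A cut patient then carries risk p/2, and

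P(at least one reaction seen) = 1 - (1 - p)^(5-k) x (1 - p/2)^k.

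For p = 0.20:

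- k = 0: 1 - 0.8^5 = 67%
- k = 1: 1 - 0.8^4 x 0.9 = 63%
- k = 5: 1 - 0.9^5 = 41%

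| p | none cut | one cut | all five cut |
|---|---|---|---|
| 0.10 | 41% | 38% | 23% |
| 0.20 | 67% | 63% | 41% |
| 0.30 | 83% | 80% | 56% |

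**What can five clean patients show?** With no events in n complete windows, the exact one-sided 95% upper bound on the event rate is 1 - 0.05^(1/n): 45.1% for n = 5, 52.7% for n = 4, 63.2% for n = 3. The gate is weak even when complete, which is a reason not to lose windows.

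**The case against.** The strongest reply is that the Day 7 data are plainly meant to exist. The calls carry no condition. SAP 4 expects every patient to attend five visits, with Visit 4 (Day 7) before Visit 5. Protocol 13.5 seeks the first week's events even from drop-outs, and there the next-transfusion limit appears to apply only beyond Day 7. The DMC is to see all safety data from the cohort, so a reasonable reader would include Visit 4. This stands as evidence of intent. It does not make the review wait for the call, and Protocol 5.5 points the other way.

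Second, a reader might infer that enrolment would reopen before the primary window has closed. The documents allow that only if several things coincide: the last patient still in follow-up is re-transfused early, the other four have finished, and the DMC gives a favourable opinion within days. No review time is stated. A cut window in a single patient needs much less.

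Third, a reader might take the fall from 67% to 41% as the size of the problem. That needs all five patients cut at 3.5 days. The only documented interval, about weekly and only in intensive treatment, falls on the Day 6 to 8 closing of the window. At two to three weeks the problem is small or nearly absent.

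Fourth, other safeguards exist. The DMC can withhold its opinion, and its charter, not among the documents reviewed, might set a minimum, although the contents listed in Protocol 3.6 do not name one. Serious events reach the sponsor within 24 hours (12.4.1), and suspected unacceptable risk requires suspension at any time (10.2). These limit the harm after the gate but do not supply the missing floor.

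**Conclusion.** The point holds as a gap in the stated rule. The gate has an upper limit and no lower one, so a cohort patient re-transfused before Day 7 can satisfy it without a complete primary safety window. The Day 7 contact that would close the gap is planned but is not a condition of the review.

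The likely size is modest. At an assumed 20% risk with even hazard, one patient cut at 3.5 days lowers the chance of seeing a reaction from 67% to 63%; 41% is the extreme with all five cut. Whether any patient is cut depends on a re-transfusion interval that the documents do not describe beyond one approximate figure for intensive treatment. The documents do not show that enrolment will reopen before Day 7, only that the rule does not prevent it. The correction is still worth making because this is the sole scheduled hold and the remedy uses a contact already planned.

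**What to change.** Keep the present endpoint and add a floor, in the synopsis Design and in SAP 4:

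> The DMC reviews the cohort once each of the five patients has reached the later of (a) the completed Day 7 (+/- 1) contact and (b) the endpoint already in force, namely the earlier of the subsequent transfusion and Day 28 (+/- 1).

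The words *the later of* matter. Triggering review at Day 7 alone would shorten the gate for anyone not yet re-transfused: if nobody is, from 5 x 28 = 140 patient-days to 5 x 7 = 35. The floor should also refer to the contact with its +/- 1 day window. A requirement of seven full days would conflict with a valid contact on Day 6.

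Reconcile Protocol 5.5 with 7.1, 11.2.1 and 13.5, so that adverse event collection runs through the Day 7 contact even after an earlier re-transfusion. Have the DMC report list, for each patient, the days of follow-up and any re-transfusion date. State how a cohort patient who dies, withdraws or cannot be reached before Day 7 is counted, so that the review does not wait for a contact that cannot happen.

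The cost is one sentence in each document, the reconciliation, and a delay of at most a few days when a cohort patient is re-transfused before Day 7. Events after re-transfusion will be harder to attribute to the study units, which is why the re-transfusion date belongs in the report. Sample size and treatment do not change.
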